### **Side Effect Monitoring.**

The research team has a clinical psychologist and physician to review initial eligibility and to monitor and address side effects during the trial. To reduce risk for adverse events, we will carefully assess eligibility to ensure that individuals with pre-existing conditions that can increase adverse event risk are excluded.

We will also frequently assess participant treatment reactions with established symptom checklists and validated suicidality and depression/anxiety scales. These assessments, as well as blood pressure assessments, are conducted at each visit before, during, and after the 12 week treatment phase by a research staff member.

We will use an established coding and reporting system for side effects also used in our ongoing varenicline trial (DA020830). In this system, personnel are trained to administer side effects measures, including validated scales of suicidality. If a side effect report or a score on an established scale indicates a safety concern, Drs. [name], [name], [name], and [name] will be notified per the Safety Monitoring and Reporting Protocol and will assume responsibility for the determination of a course of action (e.g., continue to monitor, stop medication). Participants are given contact information so that, if an adverse event occurs, they can contact study staff 24-hours a day. These side effects are also coded and managed by Drs. [name], [name], [name] and [name]. Serious adverse events are reported to the IRB, Pfizer, NIDA, and FDA in accordance with DSMP reporting procedures and participants may be referred to a PENN out-patient department or to the ER.

There are no known HAART/varenicline drug interactions (Drach et al., 2010). Varenicline is renally cleared, while the non-nucleoside reverse transcriptase inhibitors, protease inhibitors, raltegravir, and maraviroc are hepatically cleared. The nucleoside reverse transcriptase inhibitors (NRTIs) are metabolized by the kidney and, among the NRTIs, tenofovir is the only one related to risk for nephrotoxicity. HAART use will be assessed throughout the trial and patients on tenofovir will be closely monitored. We will examine the relationship between tenofovir use and varenicline side effects, including the assessment of varenicline plasma levels as a possible mediator of this relationship.

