**Table 2: Study Measures/Events**

Study Week	-1	0	1	3	5	7	9	12	18	24
Session Name	Intake	Pre-Quit	TQD	W3	W5	W7	W9	W12	W18	W24
TREATMENT										
Varenicline/Placebo		X	X	X	X	X	X	X	X	
Counseling		X	X	X	X	X	X			
SCREENING/COVARIATES										
Urine Pregnancy Screen	X									
Breath Alcohol Concentration	X									
Blood Pressure	X	X	X	X	X	X	X	X	X	X
Depression/Anxiety (HADS)	X	X	X	X	X	X	X	X	X	X
Demographics	X									
Smoking History/FTND	X									
ETOH History	X									
Medical History	X									
Psychiatric History (MINI)	X		X g							
Adherence to Antiretrovirals Instrument		X			X		X	X	X	X
Pharmacy Refill Data		X d			X d			X c		X c
Concomitant Medications	X	X	X	X	X	X	X	X	X	X
Creatinine Clearance	X a									
Viral Load Assessment								X e		
Nicotine Metabolite Ratio	X									
Genetic Polymorphisms	X									
Bipolar Disorder Symptoms (MADRS f , YMRS, Additional Screener, MINI) g	X		X	X	X	X	X	X	X	X
MEDIATING VARIABLES										
Affect (PANAS)		X	X	X		X		X		
Cognitive Function (N-back, CPT)		X	X	X				X		
Nicotine Withdrawal (MNWS-W)		X	X	X		X		X		
Smoking Urges (QSU-B)		X	X	X		X		X		
TREATMENT VARIABLES										
Adherence (Pill Count)			X	X	X	X	X	X		
Adherence (Blood)				X i				X i		
Side Effects Checklist (SEC)		X	X	X	X	X	X	X	X	X
Side Effects (Open-Ended)			X	X	X	X	X	X	X	X
Suicidality (C-SSRS)	X	X	X	X	X	X	X	X	X	X
OUTCOMES										
Carbon Monoxide (CO) Test	X	X	X	X	X	X	X	X	X	X
Smoking Rate (TLFB)		X	X	X	X	X	X	X	X	X
Urine Cotinine								X b	X b	X b
Quality of Life (HAT-QoL)		X	X	X	X	X	X	X	X	X
ACASI-SHQ h				X		X		X		
HVTN Social Impact Assessment h				X		X		X		
Client Evaluation Form h								X		

\*TQD = Target Quit Day

\*W= Week

\*Note: Target Quit Day visit may occur +3 days from target date; Week 3, 5, 7, 9, 12, 18, and 24 visits may occur +/- 1 week from target date.

a Will only be completed on initially eligible participants who have not had this test within last 6 months.

b Will only be completed on participants who self-report abstinence for  $\geq$  7 days prior to the assessment.

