#### Psychiatric History

Current and lifetime prevalence of major depression, suicidality, bipolar disorder, substance abuse or dependence, psychosis, and generalized anxiety disorder will be determined using the Mini International Neuropsychiatric Interview (MINI). The MINI (Sheehan, Lecrubier et al. 1998) is a 10-15 minute structured interview developed by the World Health Organization to assess major DSM-IV Axis 1 psychiatric diagnoses. This instrument, completed by a research staff member at the Intake Session, permits both current (past 30 days) and lifetime assessments of psychiatric illness and data support its reliability and validity (Sheehan, Lecrubier et al. 1998). Suicidality will be further assessed at each visit through the Columbia Suicide Severity Rating Scale ([www.cssrs.columbia.edu](http://www.cssrs.columbia.edu)).

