#### Depression and Anxiety

The Hospital Anxiety and Depression Scale (Zigmond & Snaith, 1983), a 14-item self-report measure, will assess depression and anxiety symptoms at each visit. This scale correlates with clinical ratings of depression and anxiety (Zigmond & Snaith, 1983) and is used with individuals with HIV/AIDS (Savard et al., 1998). This measure may be used as a mediator and a covariate.

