##### Side Effects

As in our past varenicline trials (Patterson et al., 2009; [name] et al., 2011), a checklist and open-ended questions will assess the frequency and severity of varenicline-related side effects at all time-points after the Intake Session over the course of the 24-week study, before and after medication initiation. These assessments monitor participant safety and dose reductions or suspension can occur. Side effects will be a study outcome and can be a covariate in the analysis as the overall frequency and/or as the presence (ever) of specific side effects. This measure includes psychiatric events (e.g., depressed mood, suicidal ideation; Kuehn, 2008) and cardiovascular side effects.

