**Aim 2: Assess effects of varenicline therapy on QOL and side effects.** Repeated-measures MANOVA will examine differences across treatment arms in QOL (total scale score and subscale scores) over the trial. Participant covariates will be included, such as medical treatment history. In addition, we will compare treatment arms in terms of the frequency of severe side effects (*individual, including cardiovascular side effects, and total*). Using logistic regression, we will test against the lower boundary on percent reporting only mild-moderate (i.e., < severe) side effects. The hypothesis test for equivalence is a test of whether the OR is out of the prescribed range for the difference between the treatment arms. This approach provides a more valid test of the potential safety of varenicline for individuals with HIV/AIDS vs. a simple comparison of mean responses on a side effects measure. *We will also examine if participants on tenofovir (vs. other HAART) experience a greater frequency or more severe varenicline side effects by including type of HAART as a covariate in these analyses and, if so, we can explore if this relationship is mediated by varenicline plasma levels using a regression-based path model. Lastly, we will also examine if the frequency of cardiovascular side effects is different between treatment arms while considering if participants are currently taking HAART or not by including a covariate for current HAART use in the logistic regression models of side effects.*

**Aim 3: Assess changes in affect and cognitive impairment as mediators of varenicline therapy's effect on quit rates.** We will use a regression-based path model approach to examine mediation of treatment effects based on MacKinnon et al. (2007). All variables will be standardized for the analyses. Candidate mediators include positive and negative affect and two cognitive performance task measures. Suspected mediators will be entered as standardized pre-post differences, continuously distributed and treated as normal in linear regression. The effects of treatment arm on mediators, and of mediators on outcome, will be assessed using linear regression and standardized variables. We will focus on changes in

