**Varenicline.** Some people who take varenicline may experience nausea, sleep disturbance, constipation, flatulence, and vomiting; however, these symptoms are usually mild and temporary. There have also been rare reports of erratic behavior, aggressive behavior, depressed mood, and suicidal thoughts/behavior. To minimize the likelihood of participants experiencing these side effects we will:

- Employ a stringent list of exclusionary criteria
- Administer the standard and recommended dose run-up to the 1mg B.I.D. dose
- Monitor self-reported side effects at each assessment time-point.
- Open-ended evaluation of any potential adverse events.

Study Physicians will be alerted to any severe side effects or any reported adverse events. The Study MD will review the information provided by the research staff and if applicable, will contact the study participant to gather more information and determine the appropriate course of action for the subject. Ultimately, the Study Physician will decide if the AE is related to study medication and whether the subject should discontinue taking study medication. Dose reductions, which will be tracked, may also be employed to minimize any side effect.

Varenicline may be associated with an increased risk of certain cardiac and vascular side effects, including chest pain, heart attack, and stroke. These risks are rare and are still being studied to determine how real they are. However, our study staff follows strict procedures to monitor for the presence of these side effects,

including monitoring blood pressure at each in person visit and asking specific side effect questions related to cardiovascular events (e.g. chest pain, weakness on one side, etc) during each session.

Varenicline may also be associated with new or worsening seizures during the first month of treatment. Some patients had no history of seizures, whereas others had a history of seizure disorder that was remote or well-controlled. Participants will be advised not to take Chantix if they have an unstable, untreated history of seizures.

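### No between-arm analysis of the C-SSRS is planned, and the Aim 2 comparisons capture psychiatric side effects only when rated severe, unlike cardiovascular ones

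*Combined protocol and SAP*

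**What the plan says.** **Collection.** The Psychiatric History section states: "Suicidality will be further assessed at each visit through the Columbia Suicide Severity Rating Scale". Table 2 marks the C-SSRS at every visit from Intake to Week 24 and lists it among the treatment variables, not the outcomes. The HADS is scheduled at the same ten visits.

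**Use during the trial.** Under Side Effect Monitoring, clinicians are notified "If a side effect report or a score on an established scale indicates a safety concern". This concerns the individual participant.

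**Side-effect measure.** The Side Effects section makes this a study outcome and adds: "This measure includes psychiatric events (e.g., depressed mood, suicidal ideation". Cardiovascular effects belong to the same measure.

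**Planned comparisons.** Data Analysis, Aim 2, compares severe side effects between arms, individually (cardiovascular ones included) and in total. The formal test is: "Using logistic regression, we will test against the lower boundary on percent reporting only mild-moderate (i.e., < severe) side effects". The same paragraph adds a between-arm comparison of the frequency of cardiovascular side effects, adjusted for current HAART use, with no severity threshold stated. It gives no psychiatric counterpart.

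**HADS.** The Depression and Anxiety section says: "This measure may be used as a mediator and a covariate". It is not named as a safety outcome.

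**Stated risk.** Potential Study Risks says of varenicline: "There have also been rare reports of erratic behavior, aggressive behavior, depressed mood, and suicidal thoughts/behavior".

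**The concern.** The Background argues that the safety of cessation drugs in people with HIV is unknown and has to be established, and it cites major depression in more than a third of HIV-positive patients. Aim 2 presents its severe-effect test as a more valid test of safety than a comparison of mean side-effect scores, so readers will take it as the trial's safety conclusion.

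That conclusion does not depend on sub-severe psychiatric events. A participant with new ideation graded moderate, and no severe effect of any kind, counts as favourable. The instrument designed to measure suicidality could show a difference between arms, and nothing in the statistical section commits the trial to reporting it. The plan already recognises the need for a frequency comparison in the cardiovascular domain and does not extend it to the psychiatric one.

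**Working it through.** **1. Which planned analyses can register a psychiatric event**

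| Analysis | Severe ideation or depressed mood | Mild or moderate |
|---|---|---|
| Aim 2 non-inferiority test | counts as unfavourable | counts as favourable |
| Aim 2 individual and total severe effects | counted | not counted |
| Aim 2 cardiovascular frequency | not applicable | not applicable |
| C-SSRS by arm | none planned | none planned |

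**2. The plan's own power figure**

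Inputs: 310 participants, half on varenicline, so 155 per arm. In the earlier varenicline study cited in the Power section, 76% on placebo and 61% on varenicline had no severe side effects. Alpha is 0.05 two-sided, taken as 0.025 one-sided. The documents refer only to a prescribed range, so the 15-point difference is assumed here to be the limit.

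Power with no true difference = Φ(0.15/SE − 1.96), with SE = √(2p(1−p)/155).

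- Common rate p = (0.76 + 0.61)/2 = 0.685: SE = 0.0528, Φ(2.843 − 1.960) = Φ(0.883) = 81.1%. This agrees with the stated 80%.
- p = 0.76: SE = 0.0485, Φ(3.092 − 1.960) = Φ(1.132) = 87.1%.
- At one-sided 0.05 the two figures are 88.5% and 92.6%.

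**3. Effect of a psychiatric excess on that test**

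- *Below severe:* p does not change, so non-inferiority is still concluded in about 81% to 87% of trials, however large the excess.
- *Severe:* the excess is diluted in the total. Starting from 76% on placebo, a true 5-point excess gives SE = √(0.76×0.24/155 + 0.71×0.29/155) = 0.0501 and Φ(0.10/0.0501 − 1.96) = Φ(0.038), about 52%. A 2-point excess passes in about 75%. The individual comparison could show such an excess, but no margin or power is given for it.

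**4. What a C-SSRS comparison would deliver**

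The documents give no event rates, so all rates here are assumed. Power of Fisher's exact test, two-sided 0.05, 155 per arm:

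| Any-grade event, placebo vs varenicline | All events counted | One third graded severe | One fifth graded severe |
|---|---|---|---|
| 5% vs 15% | 81% | 25% | 11% (10.5%) |
| 4% vs 12% | 69% | 18% | 6% |
| 5% vs 10% | 31% | – | – |
| 2% vs 5% | 19% | – | – |

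The second and third power columns show what is lost if only severe events are counted. For example, one third of 5% vs 15% is 1.67% vs 5%.

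Precision: with equal rates p in both arms, the approximate 95% half-width of the risk difference is 1.96√(2p(1−p)/155), or 3.1, 4.9 and 6.7 points at p = 2%, 5% and 10%.

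**The case against.** Several stronger readings are tempting, and the documents do not support them.

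- *That the non-inferiority test is the only safety comparison.* It is not. Aim 2 also compares severe side effects item by item, which would include severe ideation and severe depressed mood, and compares cardiovascular frequency.
- *That the C-SSRS goes unused or will never be tabulated.* Scores feed case-level review. The Data and Safety Monitoring section sends side-effect data, adverse events and serious adverse events to the DSMB, has that report updated at the end of the trial, and allows unblinded safety results on request. What stands is that none of this commits the trial to a C-SSRS result by arm.
- *That sub-severe events have no place at all.* The Side Effects section mentions overall frequency and the presence of specific side effects without a severity cut. That wording may refer only to covariate use, and Aim 2 builds no psychiatric comparison from it.
- *That mood is not compared between arms.* The section on positive and negative affect says the depression and anxiety scales will be mediators, and Aim 3 tests whether treatment predicts each mediator. Worsening mood could appear there. However, the Aim 3 list of candidates names only two affect and two cognitive measures, the focus is change to Week 3, and the step is not framed as safety.
- *That the severe-effect test says nothing about neuropsychiatric safety.* Severe psychiatric events do count in it.

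Context also tempers the point. The protocol calls the psychiatric reports rare, cites a meta-analysis that found insufficient evidence for serious neuropsychiatric events, and records removal of the boxed warning in December 2016. Current ideation and recent attempts are exclusions. The same meta-analysis is cited as calling for more trials in smokers with comorbidities, which this is.

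**Conclusion.** The point holds as a gap in the specified analyses. The C-SSRS has no between-arm analysis, and the Aim 2 comparisons reach psychiatric side effects only at the severe grade, while cardiovascular effects also have a frequency comparison with no stated cut. This is more than missing detail, because the stated rule places sub-severe ideation on the favourable side.

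The 81% to 87% pass rate assumes a 15-point limit, equal severe rates and one-sided 0.025. That it does not move with sub-severe events follows from the endpoint definition. It is not evidence that an excess exists.

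A reader might infer from the 81% power at 5% vs 15% that the added analysis would reliably detect harm. The documents do not support that: they give no event rates, a tripling is a large effect, and power falls to 31% and 19% for the smaller excesses. The one-third and one-fifth severe fractions are likewise illustrative. The gain is a reported estimate with an interval. No sample-size figure is affected.

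**What to change.** Add to Aim 2, by arm:

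1. The number and percent with any C-SSRS ideation or behaviour that is new or worse than the pre-dose rating, for first dose to Week 12 and separately for Weeks 18–24, with an exact confidence interval for the risk difference. Intake and Pre-Quit ratings supply the pre-dose reference.
2. The frequency of psychiatric side effects at any severity, parallel to the cardiovascular comparison.

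Optionally, report the HADS arm comparison that the mediator step already implies as a safety outcome adjusted for the pre-dose score.

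State that the severe-side-effect test does not cover sub-severe neuropsychiatric events, and present the additions as estimates with intervals rather than powered tests.

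The cost is a few sentences of analysis text and about two tables from data already collected, with no change to sample size, visits or clinical procedures. The downside is a few more safety comparisons, with wide intervals. This is a cheap improvement.

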**Varenicline Adherence.**

At each session after Pre-Quit until end of treatment, participants are evaluated in terms of their adherence by self-report and pill count. At Weeks 3 (steady-state) and 12 (end of treatment), participants will be asked to provide blood samples to evaluate varenicline levels as a measure of adherence. Specific strategies to address non-adherence will be used if necessary. The varenicline adherence approach formally assesses participant reasons for non-adherence using scenarios and uses specific strategies to enhance compliance. If the participant discontinues study medication for any reason for 14 or more consecutive days prior to an adherence blood draw, the blood draw will not be conducted.

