**Aim 1: Compare 12-weeks of varenicline treatment and behavioral counseling to 12-weeks of placebo treatment and behavioral counseling for treating nicotine dependence among individuals with HIV/AIDS.** We will analyze quit rates using mixed effects logistic regression. The model will include a term for time-point and, possibly, a *small number of covariates as needed*. The hypothesized effect of treatment arm (placebo vs. varenicline) will be tested by including a dichotomous term for treatment arm; we will also test for an interaction between time-point and treatment. Outcomes of the logistic regression analyses will be characterized by odds ratios (e.g., odds of quitting smoking) and 95% confidence intervals. Although quit-rates at the end of 12 and 24 weeks will represent our primary outcome variables, similar logistic regression analyses will be performed for other measures of quit rates, including prolonged and continuous abstinence. In addition, many participants will fail to become completely abstinent, but may show a reduction in smoking. A secondary analysis will examine the effect of treatment arm on daily cigarette counts using mixed effects negative-binomial regression. Likewise, time to (recurrent) event models will be fitted using Cox regression, stratified by event sequence, as in [name] et al. (2010b), to assess lapse and recovery events over 24 weeks.

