**Exploratory Aim: Explore participant-related variables as moderators of varenicline therapy's effect on quit rates.** These analyses will be hypothesis-generating. Variables will be chosen for this analysis based on their association with smoking behavior among those with HIV/AIDS (e.g., Webb et al., 2007). The significance of participant-related variables (e.g., mode of transmission, level of nicotine dependence, use of menthol tobacco) as moderators of varenicline's effect on quit rates can be evaluated by fitting logistic regression models relating quit rates to treatment arm and covariates. The likelihood ratio test can determine whether including such variables in the model contributes significantly to model fit. Evaluating the effect of treatment arm on quit rates by history of IV drug use, for example, is essentially doing a subgroup analysis of the interaction effect separately by such variables. To test the significance of a moderating influence of these variables, 2-way interaction terms can be added sequentially in steps of a hierarchical logistic regression model. A range of participant-related characteristics, such as socio-demographic (e.g., gender, race), psychiatric (e.g., depression), and medical (e.g., HIV/AIDS symptoms, method of HIV transmission) variables can be explored for potential interactions with treatment arm to influence quit rates at weeks 12 and 24.

**Additional Exploratory Analyses:** This trial will allow us to explore additional secondary hypotheses. One such analysis will focus on the assessment of whether HAART adherence is related to smoking cessation outcomes. [name], an expert in the assessment and evaluation of HAART adherence, will work with [name] to explore if response to varenicline, for example, affects HAART adherence or if HAART adherence is related to varenicline adherence. Prediction models of cessation outcomes (or varenicline adherence) using treatment arm and HAART adherence can be examined with logistic regression. We will also examine the relationship between 3-HC/cotinine and other variants in genes responsible for nicotine metabolism and drug target and response to varenicline for exploratory purposes.

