#### **Content of DSM Report**

The following information will be included in the DSM report:

- brief description of the trial
- baseline socio-demographic characteristics
- retention and disposition of study participants
- quality control issues
- regulatory issues
- side effect data
- adverse events
- serious adverse events
- efficacy (when sample has been collected)
- recruitment, randomization, retention, compliance, form completion, gender and minority inclusion, intervention effects, and safety.

This report will be compiled following DSM Board meetings and then updated at the trial's conclusion. In addition, adverse events experienced by participants will be reported together with participants' antiretroviral regimen to the DSMB in order for the DSMB to adjudicate safety concerns with respect to overlapping toxicities with antiretrovirals and interactions between varenicline and HAART regimen.

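### The Aim 2 tenofovir analysis names only a type-of-HAART covariate in the two-arm side-effect models, so its coefficient cannot separate a varenicline-specific excess from one common to both arms

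*Combined protocol and SAP*

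**What the plan says.** Under Data Analysis, Aim 2, treatment arms are compared on severe side effects by logistic regression. The plan then asks whether participants on tenofovir, compared with other HAART, "experience a greater frequency or more severe varenicline side effects by including type of HAART as a covariate in these analyses". A follow-on step is conditional and optional: "if so, we can explore if this relationship is mediated by varenicline plasma levels using a regression-based path model". A separate analysis of cardiovascular side effects works the same way, "considering if participants are currently taking HAART or not by including a covariate for current HAART use".

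Side Effect Monitoring gives the reason for the question. Varenicline is cleared by the kidney, and tenofovir is the one NRTI tied there to nephrotoxicity. That section plans to look at "tenofovir use and varenicline side effects, including the assessment of varenicline plasma levels as a possible mediator of this relationship", but gives no model.

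Interactions are named elsewhere, for quit rates. Aim 1 says "we will also test for an interaction between time-point and treatment", and the Exploratory Aim says "2-way interaction terms can be added sequentially in steps of a hierarchical logistic regression model". The Aim 2 side-effect text names none.

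**The concern.** The question is about effect modification. Raised varenicline exposure through reduced renal clearance can act only in people taking varenicline, so the quantity of interest is how far the varenicline-versus-placebo difference changes with tenofovir use. A covariate without a product term instead estimates a single tenofovir odds ratio shared by the two arms.

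Two misreadings follow. An excess present in both arms, from tenofovir itself or from the kind of patient who receives it, could be reported as tenofovir worsening varenicline's side effects. An excess confined to the varenicline arm would be diluted by the placebo arm, and the single arm odds ratio would hide the difference between strata. No varenicline-versus-placebo estimate is named separately for tenofovir users and users of other HAART.

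**Working it through.** The plan gives no effect size, power or sample size for this analysis, so there is no stated figure to reproduce. The check asks whether the named model can tell two different truths apart.

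**Inputs from the documents.** 310 participants, half on varenicline (Risk/Benefit Assessment), so 155 per arm. In the team's past study, 76% on placebo and 61% on varenicline had no severe side effects (Power, Aim 2), so severe rates are 24% and 39%. Two-sided alpha is 0.05 (Power).

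**Assumptions.** The share on tenofovir, s, is not given; 50% is used here, and 70% and 85% below. All tenofovir odds ratios are assumed. Arm-level rates are held at 24% and 39%, and stratum rates are solved so that (1 − s) × p_off + s × p_on equals the arm rate.

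**Two truths at s = 50%.**

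| | Placebo, off | Placebo, on | Varenicline, off | Varenicline, on |
|---|---|---|---|---|
| A: tenofovir OR 2.0 in both arms | 17.8% | 30.2% | 30.9% | 47.2% |
| B: tenofovir OR 3.5, varenicline arm only | 24.0% | 24.0% | 24.6% | 53.4% |

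With the design fixed, a main-effects logistic fit depends on the data only through the arm totals and the tenofovir totals. The arm totals are equal by construction. Among tenofovir users, the severe rate over both arms is (30.2 + 47.2)/2 = 38.7% in A and (24.0 + 53.4)/2 = 38.7% in B. Off tenofovir it is (17.8 + 30.9)/2 and (24.0 + 24.6)/2, both 24.3% after rounding. The fitted results therefore coincide: tenofovir OR 2.00, arm OR 2.06, and 78% power for the tenofovir term in either case.

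The true varenicline-versus-placebo odds ratios differ:
- A: 2.06 in both strata.
- B, off tenofovir: (0.246/0.754)/(0.24/0.76), about 1.0.
- B, on tenofovir: (0.534/0.466)/(0.24/0.76), about 3.6.

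The match is not special to large effects. A common OR of 1.5 and a varenicline-only OR of about 2.06 both give a fitted tenofovir OR of 1.50.

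**What an interaction term adds.** The arm-by-tenofovir OR is 1.0 in A and 3.5 in B. A Wald test rejects in about 5% and 69% respectively.

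**What it cannot do.** The variance of the log interaction OR is the sum over the four cells of 1/(np) + 1/(n(1 − p)). For a varenicline-only OR of 2.0 at s = 50%, each cell has 77.5 people, with rates 24%, 24%, 30.9% and 47.2%. The variance is about 0.254 and the standard error 0.504, so z = 0.693/0.504 = 1.38 and power is about 28%. At 70% and 85% on tenofovir it is about 24% and 16%.

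There is also a ceiling. Suppose tenofovir has no effect on placebo and varenicline is not protective off tenofovir (OR at least 1). With the margins held, the varenicline rate on tenofovir is then at most (0.39 − (1 − s) × 0.24)/s, which is 54.0%, 45.4% and 41.6% at s = 50%, 70% and 85%. The largest interaction OR is 3.72, 2.64 and 2.26, and power is at most about 72%, 40% and 20%.

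**The case against.** The strongest reply is that the plan is under-specified here, not wrong. Naming a covariate does not forbid a product term. A reader might infer that the plan considered and rejected an interaction; the documents do not say so. The reference to varenicline side effects, followed by a plasma-level model, might also suggest a varenicline-arm analysis, but no such restriction is stated. Without the placebo contrast, a tenofovir excess still could not be attributed to varenicline.

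The plasma-level model is a partial safeguard. It is optional, runs only if the ambiguous coefficient is positive, and addresses only the exposure pathway. It also lacks levels for some participants: when medication is stopped "for 14 or more consecutive days prior to an adherence blood draw, the blood draw will not be conducted".

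A reader might infer that participant safety depends on this coefficient. It does not. Tenofovir users are to be watched closely, the exclusion criteria remove creatinine clearance below 30 mL/min or eGFR below 60, and the DSMB receives events with regimen in order to "adjudicate safety concerns with respect to overlapping toxicities with antiretrovirals and interactions between varenicline and HAART regimen". These limit harm and make very large effects less likely, but none of them is an estimate.

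A reader might also infer that the interaction test would settle the matter, or carry the OR 3.5 example over to higher tenofovir use. With the margins held, an OR of 3.5 at 70% or 85% would require varenicline to be protective off tenofovir (OR 0.80 and 0.68), which nothing in the documents suggests. The example is therefore confined to 50%.

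**Conclusion.** The point holds for the analysis as written: the tenofovir coefficient cannot distinguish a varenicline-specific excess from a shared one. That follows from the structure of the model and does not depend on the assumed tenofovir share or odds ratios, which only illustrate its size. It is a specification gap of minor-to-moderate weight in a secondary safety question on a non-randomized factor. The primary abstinence analysis and the overall Aim 2 comparison of arms are unaffected.

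**What to change.** Among participants on HAART, add an arm-by-tenofovir term to the Aim 2 side-effect logistic models. Report the varenicline-versus-placebo odds ratio with 95% CI in tenofovir users and in users of other HAART, and label the analysis exploratory.

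The cost is one model term and one table from data already to be collected. The limits should be stated with the result:
- **Power is low:** about 28%, 24% and 16% for a varenicline-only OR of 2.0 at 50%, 70% and 85% on tenofovir. If only 80–90% of participants are on HAART (an assumption), it falls to 23–26%, 20–22% and 14–15%.
- **Intervals are wide:** for that same effect with everyone on HAART, the 95% CI multiplies and divides each stratum's odds ratio by about 2.0 at 50%. At 85% the factor is about 1.7 on tenofovir and 3.8 off it.
- **Tenofovir is not randomized:** a difference between strata may reflect who receives it.
- **A non-significant interaction is not reassurance.**

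As optional extras, the plasma-level analysis could be run in the varenicline arm without waiting for the covariate result, with a count of participants lacking a level under the 14-day rule. The main change does not depend on these.
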